Study Rationale	
Reduced exocrine pancreatic function or pancreatic insufficiency (RPF/PI) contributes to poor clinical outcome in a number of diseases and conditions. The incidence, mechanism and substantial adverse clinical outcomes of PI are well known in patients with cystic fibrosis (CF), and the life sustaining role of pancreatic enzyme medication in CF care is well established¹⁻³. Much less is known about the incidence and impact of RPF/PI in patients with chronic pancreatitis (CP). Reliable non-invasive screening or diagnostic tests with acceptable patient burden are not available for RPF/PI. We propose a study to evaluate the malabsorption blood test (MBT), stool coefficient of fat absorption (CFA) and stool bomb calorimetry (BC) methods as potential screening or diagnostic tests for RPF/PI. In subjects with CP, we also propose to administer pancreatic enzyme medication (Creon36™) to determine the test responses before and after pancreatic enzyme medication administration in these patients. Many patients with CP are at risk for RPF/PI yet they rarely undergo diagnostic testing. Pancreatic enzyme medication will likely improve clinical outcomes and quality of life in some of those with RPF/PI. A cohort of healthy volunteers will be evaluated with the three methods to provide essential comparison data to optimize the understanding and interpretation of the findings from the three methods and the RPF/PI cohort with CP.

Study Objective(s)	
Primary
 
Utilizing the MBT, CFA and BC methods to identify RPF/PI in subjects with CP, our primary hypotheses are:
 
H1: Subjects diagnosed with CP and not receiving pancreatic enzyme medication will have RPF/PI as indicated by the reduced MBT, CFA and BC fat and energy absorption pattern compared to healthy participants.
 
H2: Subjects with CP with reduced RPF/PI by the MBT, CFA and BC fat and energy absorption pattern will have improved fat absorption after pancreatic enzyme medication (Creon36™) as indicated by the MBT, CFA and BC increased fat and energy absorption pattern.
 
Secondary
 
The secondary objective of this proposal is to utilize these data to optimize the MBT design and application by reducing the time and blood samples required.
 
H3: The MBT will be optimized to identify RPF/PI with 3-4 blood samples (vs 9 current samples) over 4-5-hours (vs current 8-hours).

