Pharmacokinetic modelling will be employed to identify the three to four blood samples over the first four to five hours of the MBT that provide the most informative and most reproducible estimate of the full 8-hour MBT (nine blood samples) in the CP and healthy cohorts. The goal is a shorter sampling scheme for the MBT to optimize its use as a clinical diagnostic test. In exploratory analyses, we will compare the methods for detection of fat malabsorption as measured by CFA% and BC with fat absorption as measured by MBT for the subjects with CP compared to healthy individuals and also within the CP cohort before and after pancreatic enzyme medication use. A correlation analysis will be conducted to evaluate the performance of the MBT relative to that of the CFA%. HA and PA C_{max} , AUC, and HA/PA ratios will be plotted against CFA% or BC caloric loss to explore the relationship between the two tests. Any relationships observed in the plots will be further explored using correlation analysis and appropriate regression analysis as dictated by the observations. If a reasonable model can be developed to describe the response of MBT, CFA% and BC response to pancreatic enzyme medication treatment within the CP cohort, additional simulation studies will be performed to further examine the performance characteristics of both tests.

MONITORING PLAN

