We have shown that the MBT detects pancreatic-based fat malabsorption in healthy subjects using a lipase inhibitor medication (Orlistat)⁴⁹ and in subjects with CF and PI compared to healthy individuals and while on or off pancreatic enzyme medication treatment^{49,50}. Furthermore, the MBT can detect changes in fat absorption in subjects with CF and PI based upon the time of pancreatic enzyme administration related to food ingestion⁵⁰.

In this proposed study, we will use the MBT, CFA and BC methods to detect fat malabsorption in subjects with CP compared to healthy subjects, and the utility of the tests in detecting changes in fat absorption before and after pancreatic enzyme medication. The CFA is the “gold standard” for documenting fat malabsorption in research and in the regulatory environment. Currently CFA is the only method accepted by the FDA for evaluation of treatment of RPF/PI. Furthermore, a shorter sampling scheme for the MBT will be explored to optimize its potential use in clinical research. With these data from $n = 48$ participants including healthy comparisons and participants with varying severity of RPF/PI, pharmacokinetic methods will be employed to explore the possibility to reduce the time required and number of blood samples needed for the MBT to provide reliable classification of RPF/PI vs non-RPF/PI.

It is very likely that some patients with CP have RPF/PI and currently are not diagnosed or treated with pancreatic enzyme medication. There is no well accepted (non-invasive, acceptable patient burden, reasonably informative, and cost effective) approach to support clinical research or clinical care, nor are there established general clinical indicators or nutritional status risk factors to guide care of patients. Clinicians may avoid serious consideration of the possibility of exocrine pancreatic deterioration or just empirically try pancreatic enzyme medication. Improved care of patients with CP will be supported by additional well designed clinical research to evaluate approaches to diagnosis and establish risk factor profiles. The proposed study will contribute evidence to support future patient care in CP and physician education about RPF/PI and malnutrition in this group.

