5.2 Efficacy

5.2.2. Diagnostic tests, Scales, Measures

Malabsorption Blood Test (MBT): The **MBT primary outcomes** consist of parameters from pharmacokinetic analyses. The MBT consists of a simultaneous oral dose of pentadecanoic acid (PA), a free fatty acid, and triheptadecanoic acid (THA), a triglyceride with three heptadecanoic (HA) saturated fatty acids requiring hydrolysis by pancreatic lipase before HA can be intestinally absorbed (Patent # US 7402405 B2, July 22, 2008). The MBT with the PA and THA is delivered in a breakfast test meal after a 12-hour fast and 24 hours without dairy foods. Serum concentration

levels of PA and HA are assessed by gas-liquid chromatography (GC), from serum samples drawn prior to MBT and then hourly for eight hours. The MBT test meal is prepared immediately before consumption, with 5.0g of PA and 5.5g of THA blended into a test meal composed of 64g vanilla Scandishake (Axcan Scandipharm, Birmingham, AL), 6oz silk light chocolate soy milk, and 10ml microlipids (www.nestle-nutrition.com). The 8oz MBT test meal contains ~550 calories, 32 g fat, and 52% of calories from fat. The test meal was designed to be similar to a high fat dinner meal. Prior to administration of the MBT test meal, an indwelling catheter is placed for baseline (0 Hour) and subsequent blood draws at Hour 1, 2, 3, 4, 5, 6, 7 and 8 post ingestion for quantification of serum PA and HA. The MBT test meal is consumed within five minutes of the baseline blood draw. After the Hour 6 blood draw, subjects consume a 1000 kcal, low fat (12 g) lunch meal, and two blood samples will follow this meal (Hours 7 and 8). During the eight-hour protocol period, subjects are offered non-caloric and non-caffeinated beverages *ad libitum*. The 72-hour home stool collection will begin two days after the MBT visit, and the corresponding 3-day weighed food record will begin the day prior to the first day of the 72-hour stool collection.

Table 3. Protocol for each MBT visit

Protocol	Day 1	Day 2	Day 3	Day 4	Day 5	Day 6	Day 7	Day 8	Day 9
Enzyme-naïve: MBT #1 CP Healthy Comparisons	- Fast from 8pm - No dairy - No alcohol - Normal activity	- MBT at 8am - Lunch at 2pm - 9 hourly blood draws	Home Return to usual diet	- Diet record (day 1)	- Diet record (day 2) - 72-hour stool (day 1)	- Diet record (day 3) - 72-hour stool (day 2)	- 72-hour stool (day 3)		

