H3: Pharmacokinetic modelling will be employed to identify the three to four blood samples over the first four to five hours of the MBT that provide the best and most reproducible estimate of the full eight-hour MBT (nine blood samples) in the CP cohort and healthy comparisons. The goal is a shorter sampling scheme for the MBT to optimize its use as a clinical diagnostic test.

In exploratory analyses, we will compare the estimates of percent fat absorption from the MBT with both the CFA% from the 72-hour fecal fat and diet analysis and the BC results (energy loss in the stool). We will compare the methods for detection of fat malabsorption as measured by CFA% and BC with fat absorption as measured by MBT for the subjects with CP compared to healthy individuals and also within the CP cohort before and after pancreatic enzyme medication use. A correlation analysis will be conducted to evaluate the performance of the MBT relative to that of the CFA%. HA and PA C_{max} , AUC, and HA/PA ratios will be plotted against CFA% or BC caloric loss to explore the relationship between the two tests. Any relationships observed in the plots will be further explored using correlation analysis and appropriate regression analysis as dictated by the observations. If a reasonable model can be developed to describe the response of MBT, CFA% and BC response to pancreatic enzyme medication treatment within the CP cohort, additional simulation studies will be performed to further examine the performance characteristics of both tests.

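### H3 says the short MBT will identify RPF/PI, but its analysis shows only how well 3-4 samples reproduce the full MBT that contains them

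*Combined protocol and SAP*

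**What the plan says.** **Target.** H3 in the Protocol Synopsis (Study Objectives) reads: "The MBT will be optimized to identify RPF/PI with 3-4 blood samples", over 4-5 hours instead of 8. Section 1.5 Relevant Literature gives the purpose of the shorter scheme as "to provide reliable classification of RPF/PI vs non-RPF/PI".

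**Analysis.** Section 6.3.1 Efficacy Analysis (H3) uses pharmacokinetic modelling to pick 3-4 draws from the first 4-5 hours. The draws to be picked are those that "provide the best and most reproducible estimate of the full eight-hour MBT", and the text names both cohorts. The synopsis gives nearly the same criterion.

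**Source of the samples.** Section 5.2.2 takes one baseline draw and "subsequent blood draws at Hour 1, 2, 3, 4, 5, 6, 7 and 8 post ingestion". The short schedule is therefore a subset of the nine draws that it is judged against.

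**What is not stated.** The H3 analysis names no RPF/PI reference, cut-off, ROC area, sensitivity, specificity or success rule. The exploratory comparisons with CFA% and BC in the same section concern the MBT in general and do not mention the short schedule. The simulation of performance characteristics is conditional on a reasonable model of the response to enzyme treatment.

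**The concern.** H3 makes a diagnostic claim, but its analysis measures agreement. The two can come apart. A short schedule may track the eight-hour value well because it shares samples with it and because neighbouring hourly values are alike, and still lose part of the difference between groups or conditions. This matters if that difference lies partly in the later hours. Section 5.2.2 explains that HA must be released by lipase before it is absorbed, whereas PA is a free fatty acid, so a timing difference is conceivable. The documents do not report one.

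At stake is the use to be made of the result. Section 6.3.1 says the shorter scheme is meant for use as a clinical diagnostic test. As planned, the trial would name a best 3-4 sample schedule without reporting whether that schedule separates the groups, or responds to Creon36, as the nine-sample test does.

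**Working it through.** H3 has no sample size, threshold or success rule, so there is no H3 figure to reproduce. The H1 effect in 6.4 Sample Size and Power is used for scale.

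**1. The H1 effect.** Difference 0.60, SD 0.68, 22 per group, alpha 0.05 taken as two-sided. d = 0.60/0.68 = 0.88. The exact t-test power is 81.6%, consistent with the stated 80%. With normal data and equal SDs, ROC area = Φ(d/√2) = Φ(0.624) = 0.73.

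**2. Agreement from shared samples (illustration).** Assume that the eight-hour AUC is the sum of eight hourly increments with equal variance and no correlation. The first k increments then correlate with the total at √(k/8):
- k = 4: √0.5 = 0.71
- k = 5: √0.625 = 0.79

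These values arise although the short AUC carries no information on the later hours. The independence assumption is not from the documents. If increments j hours apart instead correlate at 0.8^j, the variance of the sum is 38.71 for eight increments, 12.38 for four and 18.11 for five. The covariance of the short sum with the total is 19.36 (k = 4) or 24.67 (k = 5):
- k = 4: 19.36/√(12.38 × 38.71) = 0.88
- k = 5: 24.67/√(18.11 × 38.71) = 0.93

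**3. Can an informative full test give an uninformative short one?** Worst case: the full AUC separates equal groups by d = 0.88 SD, and all of this arises after the short window. The correlation over all subjects is then the within-group correlation divided by √(1 + d²/4) = √(1 + 0.195) = 1.093, that is, multiplied by 0.915.

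| Increments | Window | Within group | All subjects | ROC area, full | ROC area, short |
|---|---|---|---|---|---|
| Independent | 4 h | 0.71 | 0.65 | 0.73 | 0.50 |
| Independent | 5 h | 0.79 | 0.72 | 0.73 | 0.50 |
| 0.8^j | 4 h | 0.88 | 0.81 | 0.73 | 0.50 |
| 0.8^j | 5 h | 0.93 | 0.85 | 0.73 | 0.50 |

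Complete loss of separation lowers the correlation by less than a tenth of its value.

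**4. Selection in the same data.** There are C(6,3) + C(6,4) = 20 + 15 = 35 schedules of 3-4 samples from hours 0-5. In 2,000 simulated trials of 48 subjects, with independent hourly values unrelated to group, the best schedule has an expected correlation with the full AUC of 0.69. Picking the best of 35 in each data set raised the mean observed value to 0.75. Over assumed hour-to-hour correlations of 0 to 0.95, the selected schedule correlated 0.75 to 0.99 with the full AUC, with a mean ROC area of 0.50. Because the full test was uninformative too, this run shows only that agreement is not itself evidence of separation. Step 3 covers the informative case.

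**5. Attainable precision.** For a ROC area of 0.73 with 22 per group, the Hanley-McNeil standard error is 0.076, giving 0.73 ± 1.96 × 0.076, or about 0.58 to 0.88.

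**The case against.** The strongest reply is that the plan works in two linked steps. H1 and H2 test whether the full MBT separates CP from healthy and off from on enzyme, and exploratory work relates it to CFA% and BC. H3 then looks for a shorter version of that test. Approximating a longer test is a legitimate goal of reduced sampling, and with about 22 per group it is a more stable basis for selection than ROC area, which would be optimistic when maximised over many schedules. This stands, and the planned selection should be kept. A reader might infer that agreement with the full MBT is the wrong criterion altogether. The documents do not support that.

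Other parts of the reply also stand:
- A reader might infer that agreement is to be judged in CP and healthy subjects pooled. Section 6.3.1 names both cohorts but does not say whether they are pooled or reported separately.
- Late absorption in CP would itself lower agreement, so the planned criterion would penalise it. Step 3 shows that the penalty can be small, but only under assumed conditions.
- The plan specifies pharmacokinetic modelling, and the MBT outcomes include Cmax and HA/PA ratios. A truncated AUC is a simplification.
- Sections 2.2 and 6.2 state the secondary aim as saving time and samples, which the analysis does address, and 1.5 speaks of exploring a possibility.

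The reply does not close the gap. A valid full test and good agreement together do not establish that the short test separates, and no planned analysis reports whether it does.

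**Conclusion.** The concern holds as a mismatch between H3 as worded, with the classification purpose in 1.5, and the H3 analysis in 6.3.1. It follows from the text and needs no assumption. Its numerical consequence is unknown. The 0.71-0.79 correlations and the fall in ROC area from 0.73 to 0.50 are illustrations under assumed correlation structures and, for the latter, an extreme placement of the group difference. Neither predicts what this trial will find.

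A reader might go further and infer that H3 could be declared met by a test without diagnostic value. The documents do not support that wording, because H3 has no success rule. The plan only reports a best schedule, and some schedule will always be best.

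CP versus healthy is itself only a proxy for RPF/PI. Section 1.5 expects varying severity, and 9.4.2 allows for normal pancreatic function in some enzyme-naive CP subjects. The point concerns a secondary aim and leaves H1 and H2 untouched. It is worth correcting because the data are already being collected.

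**What to change.** In 6.3.1 Efficacy Analysis (H3), keep the planned selection. Then report for the selected schedule:

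1. The ROC area for CP off enzyme versus healthy, and the standardised paired change off versus on Creon36. Give each as a difference from the nine-sample MBT with a 95% CI that allows for selection in the same data, for example a bootstrap or cross-validation that repeats the selection.
2. Agreement with the eight-hour value separately for healthy, CP off enzyme and CP on enzyme.
3. The relation of the short MBT to CFA%, which 1.5 describes as the historical gold standard and which Table 1 collects in both cohorts.

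If this is not done, reword H3 to claim only agreement with the full MBT.

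The cost is plan wording and further analysis of existing profiles, with no added subjects, visits or samples. The drawback is wide intervals at about 22 per group (roughly ±0.15 for a single ROC area; a paired difference between schedules should be narrower). The results should be presented as estimates, not as proof that the short test is equivalent.

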2.2 Secondary Aims

2.2.1. The **secondary aim** of this proposal is to utilize these data to optimize the MBT design and application by reducing the time and blood samples required.

2.2.2. We will also **explore** the utility of the MBT compared to the CFA and BC (both require the burdensome 72-hour total stool and dietary intake collection) in identifying differences in fat absorption between subjects with CP and healthy individuals and within the CP cohort, with and without pancreatic enzyme medication.

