6.3.1 Efficacy Analysis

Statistical Analysis: H1 and H2: Descriptive statistics for MBT, CFA% and BC outcomes (mean, standard deviation, median, range, 95% CI) will be calculated for the CP cohort and for the healthy comparison group, and differences between CP and healthy groups assessed with unpaired t tests. For the MBT outcomes, a moment-based pharmacokinetic (PK) analysis will be performed based on non-compartmental methodology using WinNonLin version 9.1 (Pharsight, Cary, NC). Baseline (C_0) and maximum (C_{max}) plasma concentrations are calculated, and area under the curve from time zero to eight hours (AUC) is calculated using the linear trapezoid method. PK parameters can then be compared between treatment groups using a paired t-test or Wilcoxon signed rank test as appropriate. To describe HA exposure relative to that of PA, the ratio of the HA to PA C_{max} (C_{max} HA/PA) and AUC (AUC HA/PA) is calculated for each subject after molar transformation and dose-normalization of exposure metrics⁴⁹. Alternately, population PK analyses for repeated-measures endpoints can be conducted via nonlinear mixed-effects modeling with a qualified installation of the nonlinear mixed-effects modeling (NONMEM) software, Version VII, Level 2.0 (ICON

Development Solutions, Hanover, MD)⁴⁸. Using this method, population PK modeling is conducted by simultaneously fitting structural PK models to both PA and HA concentrations⁵⁰.

Descriptive statistics for MBT, CFA% and BC outcomes (mean, standard deviation, median, range, 95% CI) will also be calculated for the CP cohort with and without pancreatic enzyme medication administration, and the significance of changes over time assessed with paired t tests. HA and PA concentrations will be transformed to molar quantities and the ratios for HA to PA C_{max} and AUC and the associated 95% confidence interval will be calculated. A mixed effects modeling approach will be employed to examine the correlation of subject characteristics (age, BMI, sex, disease status, etc.) to PA and HA exposure metrics derived from the non-compartmental analysis to assess change over time in MBT response to pancreatic enzyme medication administration in subjects with CP. Metrics to be tested will be CFA%, PA and HA C_{max} , AUC, HA/PA C_{max} and AUC ratio and the %HA response compared to the healthy reference group. A value of $p < 0.05$ will be considered statistically significant.

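### Beyond one unspecified MBT-CFA% correlation, MBT-versus-stool correlations and regressions are planned only where a plot of the same data shows a relationship, so which pairings get estimated depends on the results

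*Combined protocol and SAP*

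**What the plan says.** The exploratory part of section 6.3.1 (Efficacy Analysis) runs in this order:

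1. A comparison with no condition attached: "In exploratory analyses, we will compare the estimates of percent fat absorption from the MBT with both the CFA"% and with the BC results. The methods are also to be compared between CP and healthy subjects, and within CP before and after enzyme.
2. A correlation with no condition attached: "A correlation analysis will be conducted to evaluate the performance of the MBT relative to that of the CFA"%. No MBT metric, cohort, visit or coefficient is named.
3. Plots: HA and PA Cmax, AUC and the HA/PA ratios "will be plotted against CFA% or BC caloric loss to explore the relationship between the two tests".
4. The follow-up rule: "Any relationships observed in the plots will be further explored using correlation analysis and appropriate regression analysis as dictated by the observations".
5. A conditional simulation, which concerns the subjects with CP only. The condition reads: "If a reasonable model can be developed to describe the response of MBT, CFA% and BC response to pancreatic enzyme medication treatment". If it is met, the plan is that "additional simulation studies will be performed to further examine the performance characteristics of both tests". No criterion for a reasonable model is given.

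The synopsis (Statistical and Analytic Plan) repeats steps 2 to 5 almost unchanged. The work serves item 2.2.2 of the secondary aims, which is to explore "the utility of the MBT compared to the CFA and BC". The only significance rule is in the H1/H2 part of section 6.3.1: "A value of $p < 0.05$ will be considered statistically significant". No multiplicity rule is given for the exploratory pairings.

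**The concern.** Step 4 is a selection rule. A pairing whose plot shows a pattern gets a correlation and a regression. A pairing whose plot shows nothing has no planned estimate, apart from whatever the single correlation in step 2 turns out to cover. The interval and p value from a selected pairing take no account of the selection, and the model form is fitted to the pattern that prompted it.

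Step 2 closes the gap only in part. With six MBT metrics and several possible populations, the one unconditional correlation can still be chosen after the data are seen. For BC, only an unspecified comparison is unconditional.

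At stake is how aim 2.2.2 can be read. Section 1.5 treats CFA as the reference method in research and regulation, and step 2 says the correlation is meant to evaluate MBT performance. A reader of the results needs to know how many pairings were examined and how many showed nothing. The plan does not ensure that.

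**Working it through.** The documents give no figure for these analyses, so there is none to reproduce. The check asks how often chance alone would offer something to follow up.

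**Inputs from the documents**
- Evaluable subjects: 22 per group (section 3.3.2), so 44 if pooled.
- MBT metrics: HA Cmax, PA Cmax, HA AUC, PA AUC, HA/PA Cmax, HA/PA AUC. This is my count from section 6.3.1.
- Stool outcomes: CFA% and BC. Pairings per set: 6 × 2 = 12.
- Significance level: two-sided 0.05.

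**Inputs assumed:** the correlations among MBT metrics and between CFA% and BC, which the documents do not give. A range is shown.

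**Threshold.** r_crit = t / √(n − 2 + t²). At n = 22, t = 2.086 on 20 df, so r_crit = 2.086 / √(20 + 4.351) = 0.423. At n = 44 it is 0.297.

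**Independent pairings.** 1 − 0.95¹² = 0.46.

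**Correlated pairings.** Simulation with 20,000 data sets per row, n = 22, and no true MBT-stool association. The last column is the median of the largest r in absolute value.

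| Correlation among MBT metrics | CFA-BC correlation (size) | Any p<0.05 | Median largest r |
|---|---|---|---|
| 0 | 0 | 46% | 0.41 |
| 0 | 0.7 | 41% | 0.40 |
| 0.5 | 0 | 38% | 0.39 |
| 0.5 | 0.7 | 33% | 0.37 |
| 0.8 | 0 | 27% | 0.34 |
| 0.8 | 0.7 | 23% | 0.32 |

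When at least one pairing is significant, the largest r averages about 0.50 in every row. At n = 44 the range is 46% down to 22%, and the corresponding average is about 0.36.

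**A more structured case.** Here the ratios are built from the simulated HA and PA values, with Cmax-AUC correlation 0.80 to 0.85, PA-HA correlation 0.4 to 0.5, and CFA-BC correlation −0.6. At n = 22:
- at least one of the 12 pairings has p<0.05 in about 30% of data sets, and the largest r averages about 0.37 in absolute value over all data sets;
- a correctly signed HA or HA/PA pairing (positive with CFA%, negative with BC energy loss) reaches the threshold in about 12%;
- a correctly signed HA/PA ratio versus CFA% does so in about 4%.

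**Why the population must be named.** Pooling the groups creates a correlation from the group difference alone. With the planned differences in section 6.4, d₁ = 0.60/0.68 = 0.882 (MBT) and d₂ = 10/11 = 0.909 (CFA%). With no association within either group, r = (d₁d₂/4) / √[(1 + d₁²/4)(1 + d₂²/4)] = 0.2005 / √(1.1946 × 1.2066) = 0.17. This is significant in about 20% of simulated trials with 44 subjects.

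**The case against.** The strongest reply is that this is declared exploratory work in a study that calls itself exploratory. Looking at plots before choosing a model form is ordinary practice, and H1, H2 and H3 do not depend on it. That stands, and it keeps the point minor. It does not answer the selection issue, because exploration can be reported with its denominator at almost no cost.

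It is also true that the paragraph contains unconditional steps, and that the plot rule speaks of exploring further. A reader might infer that no MBT-stool relationship is tested unless a plot shows one. The text does not support that for CFA%: a correlation is planned outright, though unspecified. Nor does anything say that null pairings will be withheld.

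Two other inferences are tempting. One is that the plot-derived regression feeds the simulation of test performance. The documents tie the simulation to a model of response to enzyme treatment in the CP cohort and do not say that this is the MBT-versus-stool regression. The other is that chance patterns will be presented as validation of the MBT. No planned text says so.

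Finally, the 30% figure counts PA-only pairings and wrong-signed correlations. Section 1.5 says PA does not need pancreatic lipase, so a chance PA correlation would hardly be read as support for the test. That objection is fair, and the figure of about 12% is the better guide to misleading support for the MBT.

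**Conclusion.** The point holds in a limited form. Follow-up correlation and regression of the MBT metrics against CFA% or BC is conditional on plots of the same data, with the model form taken from those plots. The one unconditional correlation leaves metric and population open, and BC has none.

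With no true association and 22 subjects, the chance of at least one nominally significant pairing per set is roughly 22% to 46% over the assumptions tried. It is about 30% under the structured assumptions, and about 12% for pairings that would look like support for the MBT. A selected significant correlation would average about 0.50. These figures rest on the count of 12 pairings and on assumed correlations that the documents do not supply. They describe what selection could produce, not what the investigators are planning to report. Severity is low: a worthwhile improvement to an exploratory analysis.

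**What to change.** Replace the plot-triggered rule in section 6.3.1 and the synopsis with the following:

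- Estimate and report all 12 listed pairings, with r and 95% CI, in each fixed set (healthy, CP Visit 1, CP Visit 2), whatever the plots show.
- Name in advance one HA/PA ratio versus CFA% as the main pairing, and the set in which it is read. Section 6.4 uses both Cmax and AUC ratios, so the sponsor can choose either. The chance of a false p<0.05 for that pairing is then 5%.
- Use the plots only to check linearity and outliers.
- Label the remaining pairings exploratory and unadjusted.
- If the treatment-response simulation is run, state what makes a model reasonable and carry the uncertainty of the fitted model into the stated performance, for example by a bootstrap over subjects.

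The cost is a few sentences and one more table, with no new data. The downside is that more null correlations will be on show.
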